7.3. Lifestyle Restrictions**7.3.1. Meals and Dietary Restrictions**

Refrain from consumption of food or drinks (except water) for 8 hours prior to visits that require blood draws for bone biomarkers.

7.4. Screen Failures

Screen failures are defined as participants who consent to participate in the clinical study but are not subsequently randomised. A minimal set of screen failure information is required to ensure transparent reporting of screen failure participants to meet the Consolidated Standards of Reporting Trials (CONSORT) publishing requirements and to respond to queries from regulatory authorities. Minimal information includes demography, screen failure details, eligibility criteria, and any serious adverse events (SAE) and adverse events of special interest (AESI).

Individuals who do not meet the criteria for participation in this study (screen failure) may not be rescreened.

However, the screening period may be extended beyond 28 days in the following circumstances with the discussion and with the approval of the medical monitor:

- All screening inclusion/exclusion criteria are met but the participant's schedule, including genetic testing or HRpQCT scan, prevented them from being randomised within the screening period.

Additionally, individual lab parameters or screening test may be repeated if the result is considered aberrant or not clinically consistent with the patient's health status. Decisions to re-test should be made in conjunction with the study medical monitor.

Participants who have individual laboratory parameters re-tested should have the results entered in the electronic case report form (eCRF).

8. Treatments

Study treatment is defined as any investigational treatment(s), marketed product(s), placebo, or medical device(s) intended to be administered to a study participant according to the study protocol.

8.1. Treatments Administered

Study Treatment Name:	Setrusumab	Concomitant Vitamin D and Calcium Therapy	Zoledronic Acid
Dosage Formulation:	Lyophilised powder for solution	Calcium tablets and Vitamin D capsules	Solution for infusion
Unit Dose Strength(s)/Dosage Level(s):	150 mg	500mg Calcium and 800 IU Vitamin D	4 mg single dose
Route of Administration:	IV	Oral	IV
Dosing Instructions:	60-minute infusion	Oral with water	15-minute infusion
Packaging and Labelling:	Study Treatment will be provided in labelled vials packed into in cartons containing 20 vials. Each vial and carton will be labelled as required per country requirement	Not applicable	Stocks will be labelled with study information and standard packaging.
Responsible Manufacturer:	Mereo Biopharma 3 Ltd, [name]	Provided by Investigational sites	Provided by Mereo Biopharma 3 Ltd, [name]

8.1.1. Zoledronic acid therapy

Following the end of setrusumab therapy all participants will have the option to receive a dose of zoledronic acid at 12 and 18 months. This will be prescribed at the discretion of the treating physician and in line with local guidelines.

8.2. Method of Treatment Assignment

All participants will be centrally randomised using an Interactive Web Response System (IWRS) in a 1:1:1:1 ratio to receive either 20 mg/kg, 8 mg/kg, 2 mg/kg or open-label 20 mg/kg. Subject to informed consent being given by the participant, all participants assigned to placebo prior to protocol amendment 4.0 will be reassigned to begin 12 months of open-label 20 mg/kg setrusumab treatment. ICON Biostatistics will produce a randomisation list that links participant numbers to randomisation numbers. These randomisation numbers will be linked to different treatment regimens and the randomisation scheme will be stratified according to the Sillence Clinical Classification of OI type into 2 groups (Type I or III/IV).

Following confirmation from the investigator, the pharmacist will contact the IWRS and be issued with a treatment regimen. Should the participant be allocated to a setrusumab regimen, then the pharmacist will input the patient's weight into the IWRS and receive a calculated dose per participant.

Before the study is initiated, the web address for the IWRS and the log in information & directions will be provided to each site.

Study treatment will be dispensed and dosed at the study visits summarised in the Schedule of Activities.

8.3. Blinding

With the exception of the open-label treatment arm, investigators and participants will remain blinded to each participant's assigned study treatment throughout the course of the study. In order to maintain this blind, an otherwise uninvolved 3rd party (pharmacist) will be responsible for the reconstitution and dispensation of all study treatment. A separate unblinded Clinical Research Associate (CRA) will monitor the pharmacy.

In the event of a Quality Assurance audit, the auditor(s) will be allowed access to unblinded study treatment records at the site(s) to verify that randomisation/dispensing has been performed accurately.

The IWRS will be programmed with blind-breaking instructions. The study blind may be broken if, in the opinion of the investigator, it is in the participant's best interest to know the study treatment assignment. Mereo must be notified before the blind is broken unless identification of the study treatment is required for a medical emergency in which the knowledge of the specific blinded study treatment will affect the immediate management of the participant's condition (eg, antidote is available). In this case, Mereo must be notified within 24 hours after breaking the blind. The date and reason that the blind was broken must be recorded in the source documentation and eCRF, as applicable.

8.4. Preparation/Handling/Storage/Accountability

The investigator or designee must confirm appropriate temperature conditions have been maintained during transit for all study treatment received and any discrepancies are reported and resolved before use of the study treatment

On written confirmation by the investigators, the pharmacist will contact the IWRS, enter the participant number and weight. The IWRS will inform the pharmacist of the treatment allocation

and dose required for the participant, based on their weight. The IWRS will provide the number of vials required to reconstitute and mix the appropriate dose for the participant. The pharmacist will select and record the vials used to reconstitute and mix the dose in the IWRS.

Further details of the preparation and administration of the study treatment, please refer to the Study Treatment Administration Guide and the MBPS205 Pharmacy Manual.

Only participants enrolled in the study may receive study treatment and only authorised site staff may supply or administer study treatment. All study treatments must be stored in a secure, environmentally controlled, and monitored (manual or automated) area in accordance with the labelled storage conditions with access limited to the investigator and authorised site staff.

The investigator, institution, or the head of the medical institution (where applicable) is responsible for study treatment accountability, reconciliation, and record maintenance (ie, receipt, reconciliation, and final disposition records).

Further guidance and information for the handling, disposition and accountability of study treatment are provided in the MBPS205 Pharmacy Manual.

8.5. Treatment Compliance

The per protocol dosage, timing and mode of administration of study medication may not be changed. Any departures from the intended regimen must be recorded in the eCRF and notified to the sponsor.

8.6. Concomitant Therapy

Concomitant Vitamin D and Calcium Therapy

Vitamin D levels should be 50 nmol/L or higher during the study. If less than 50 nmol/L at screening the participant should be treated as per the local guidelines and retested during the study to maintain vitamin D levels above 50 nmol/L. Calcium levels should be in the normal range for study entry. For the duration of the study participants can, if required, receive a daily dose of 500 mg calcium and/or 800 I.U. vitamin D as background treatment, but if the participant already receives a higher dose, they can stay on the dose they receive. Calcium tablets should not be taken 2 hours prior to DXA lumbar scan.

The following classes of medication listed below are not permitted to be taken during the conduct of the study starting from screening (for details of screening criteria concerning medications, see [Section 7.2](#)):

1. Bisphosphonates (oral and injectable)
2. RANKL antibodies (Denosumab)
3. PTH and analogues
4. All other monoclonal antibodies
5. Medications known to affect bone physiology (e.g. aromatase inhibitors)
6. Systemic corticosteroid drugs

Physical aids and physiotherapy are explicitly allowed. Treatment with zoledronic acid during the follow-up period is explicitly allowed at Months 12 and 18 only at the discretion of the treating physician.

Any medication or vaccine (including over-the-counter or prescription medicines, vitamins, and/or herbal supplements) that the participant is receiving at the time of enrolment or receives during the study must be recorded along with:

- reason for use
- dates of administration including start and end dates
- dosage information including dose and frequency

All other concomitant medications are allowed, unless they are explicitly not allowed or are known to affect bone or bone metabolism.

The ICON Medical Monitor can be contacted if there are any questions regarding concomitant or prior therapy.

8.7. Treatment After the End of the Study

Participants completing the MBPS205 study will be able to discuss other potential treatments for their osteogenesis imperfecta with their investigators when they complete the 12-month follow up period at the end of MBPS205.

9. Discontinuation Criteria

9.1. Discontinuation of Study Treatment

Participants may voluntarily discontinue investigational treatment for any reason at any time. If the participant no longer wants to take part in the study, they will be asked to attend an end of treatment visit and 60-day follow-up visit and be discontinued from the study.

The investigator should discontinue investigational treatment of a given participant if, on balance, he/she believes that continuation would be detrimental to the participant's well-being. However, the participant should be followed up to the end of the study and all study procedures should be performed per protocol.

Investigational treatment must be discontinued under the following circumstances and then further steps need to be discussed with the medical monitor:

1. Anaphylactic reaction or other severe systemic reaction to study drug injection
2. Diagnosis of malignancy during study
3. Evidence of pregnancy
4. Absolute corrected QT interval (QTc) corrected using Fridericia's formula (QTcF) is >500 msec and rise from baseline, confirmed by triplicate ECGs, is ≥ 60 msec (Refer to [Section 10.4.3](#))
5. Any of the following confirmed laboratory abnormalities:
 - Renal function values that require discontinuation:
 - Discontinue investigational treatment for a participant if individual serum creatinine increases $\geq 50\%$ compared to baseline (and is considered clinically significant), or in the event of treatment-emergent proteinuria (albumin: creatinine ratio > 300 mg/g or > 30 mg/mmol; protein: creatinine ratio (PCR) ≥ 500 mg/g or > 50 mg/mmol), unless the event is not drug related, or if the risk/benefit assessment supports continuing investigational treatment.

Note: A renal event leading to participant discontinuation should be followed up until event resolution (serum creatinine within 10% of baseline, PCR within 50% of baseline), stabilises or becomes not clinically significant, or is assessed as being chronic.

- Liver laboratory values that require discontinuation
 - Confirmed alanine aminotransferase (ALT) or aspartate aminotransferase (AST) > 5 times the upper limit of normal (ULN) (for more than 2 weeks)
 - Confirmed ALT or AST > 3 times the ULN and confirmed bilirubin total > 2 times ULN (unless elevated bilirubin is related to confirmed Gilbert's syndrome)

Note: If the laboratory abnormality is considered causally related to study drug, study treatment will be permanently discontinued. In cases in which a causal relationship to study drug can be reasonably excluded, (ie, an alternative cause is evident), study treatment will be discontinued but it may be resumed when the laboratory abnormality is sufficiently normalised. A decision to resume study treatment will be made jointly by the investigator and medical monitor (medical monitor's written approval is required).

6. Withdrawal of informed consent
7. Significant non-compliance of the participant with study procedures
8. Sponsor decision

If a clinically significant finding is identified (including, but not limited to changes from baseline in QTcF after enrolment; the investigator or qualified designee will determine if the participant can continue in the study and if any change in participant management is needed. This review of the ECG printed at the time of collection must be documented. Any new clinically relevant finding should be reported as an AE.

Refer to the [SoA](#) for data to be collected at the time of treatment discontinuation and follow-up and for any further evaluations that need to be completed.

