9.1.1. Temporary Discontinuation

Study drug dosing may be temporarily suspended in the event of:

1. Clinically important laboratory abnormalities
2. Other intercurrent illnesses or major surgery
3. Use of prohibited treatment
4. Any other protocol deviation that results in a significant risk to the participant's safety
5. Sponsor decision

After a laboratory abnormality leading to a delay of dosing normalises sufficiently, study treatment may resume at the discretion of the principal investigator in consultation with the medical monitor. Similarly, study treatment may resume after the medication leading to suspension of dosing is discontinued. A decision to discontinue study drug and/or to reinstitute study treatment should be discussed with the medical monitor. The investigator may suspend study treatment at any time, even without consultation with the medical monitor if the urgency of the situation requires immediate action and if this is determined to be in the participant's best interest. However, the medical monitor should be contacted as soon as possible in any case of study drug discontinuation.

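### As worded, Protocol 9.1 item 5 gives two different instructions for the same renal abnormality: the renal bullet allows treatment to continue in two cases where the closing note requires it to stop

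*Protocol*

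**What the plan says.** Protocol section 9.1 opens its list of stopping rules in mandatory terms: "Investigational treatment must be discontinued under the following circumstances and then further steps need to be discussed with the medical monitor". Item 5 of that list is headed "Any of the following confirmed laboratory abnormalities" and has a renal part and a liver part.

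The renal bullet begins "Discontinue investigational treatment for a participant if individual serum creatinine increases" by at least 50% from baseline and the rise is considered clinically significant. It gives treatment-emergent proteinuria as the alternative trigger. It then adds an exception: "unless the event is not drug related, or if the risk/benefit assessment supports continuing investigational treatment". A short note on follow-up, expressly about renal events, comes next.

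The liver bullets follow, with no causality exception apart from the carve-out for Gilbert's syndrome. A second note then closes item 5. For a related abnormality it says: "If the laboratory abnormality is considered causally related to study drug, study treatment will be permanently discontinued". For an unrelated one it says: "In cases in which a causal relationship to study drug can be reasonably excluded", "study treatment will be discontinued but it may be resumed when the laboratory abnormality is sufficiently normalised". The decision to resume is made jointly by the investigator and the medical monitor, and the medical monitor must approve in writing.

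Section 9.1.1 deals with optional temporary suspension, including for clinically important laboratory abnormalities. Once the abnormality has normalised sufficiently, "study treatment may resume at the discretion of the principal investigator in consultation with the medical monitor". Section 9.1.2 adds that resumption is always to be discussed with the medical monitor.

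The SAP contains no rule that settles how these texts fit together.

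**The concern.** A site with a confirmed renal result that meets the trigger can find two instructions within the same numbered item. If it applies the renal bullet, an unrelated event need not lead to stopping, and a related event may be continued through on a risk/benefit judgement. If it applies the closing note, treatment stops in both situations, permanently in the second.

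The first consequence is for participant safety, because a stopping rule should lead to the same action at every site. The choice of text also decides whether the medical monitor is brought in under section 9.1. The duty to discuss further steps there follows a discontinuation, and under the renal exception there is none. The renal bullet does not say who makes the risk/benefit assessment.

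There are smaller consequences for the analysis. SAP section 8.6.1 tabulates adverse events leading to permanent discontinuation by treatment group, and Protocol section 6.5 bases dose selection on HRpQCT results and safety. Per-protocol membership (Protocol 11.2, SAP 6.4) requires treatment according to the protocol. A participant who continues after a renal trigger would comply with the renal bullet but deviate from the closing note.

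**Working it through.** No arithmetic applies. The check takes one confirmed renal result that meets the trigger and applies the two texts of item 5 to it in each case.

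| Case | Renal bullet | Closing note, read as covering renal values | Agree on stopping? |
|---|---|---|---|
| Not drug related | No duty to discontinue | Discontinue; may resume after normalisation with written approval | No |
| Drug related, risk/benefit supports continuing | No duty to discontinue | Discontinue permanently | No |
| Drug related, risk/benefit does not support continuing | Discontinue | Discontinue permanently | Yes |

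The texts disagree in two of the three cases, and these are the two that the renal exceptions were written to cover. In the first case the stop required by the note can be reversed, so the disagreement is about whether to stop at all. In the second it is between continuing and stopping for good.

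The next question is whether the wording takes renal values out of the closing note.

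1. The note speaks of the laboratory abnormality in general. That matches the common header of item 5, which covers both renal and liver values.
2. The earlier note in item 5 names renal events expressly. The closing note names neither organ.
3. If the closing note is nevertheless for liver values only, item 5 says nothing on whether a renal stop is permanent or how treatment could resume. Only section 9.1.1 would then be left to apply.

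The wording therefore leaves the scope open, and on the liver-only reading a different gap appears.

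Two lesser points arise from the same text:

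- **Resumption route.** The closing note requires a joint decision and written approval. Section 9.1.1 leaves resumption to the principal investigator's discretion in consultation with the medical monitor. Section 9.1.1 does not say that item 5 events fall outside it.
- **Inequality signs.** The protein:creatinine trigger is at least 500 mg/g in one unit and more than 50 mg/mmol in the other. The albumin:creatinine trigger uses a strict inequality in both units.

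**The case against.** The strongest reply is that the conflict disappears on a sensible reading of the layout. The renal block has its own trigger, exceptions and note. The liver block follows, and then a second note. One note per block is a natural structure, and the liver bullets are the ones that lack a relatedness rule. Alternatively, a renal result that falls within the exceptions is not one that requires discontinuation, so the closing note is never reached. Indentation lost in the text extraction might also have shown which block the note belongs to.

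Both readings are plausible, so a reader should not infer that the protocol's authors set two rules against each other, or that the note certainly overrides the exceptions. What remains is that neither limit is written down, and a site that follows the words as they stand could act either way.

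Three stronger inferences are tempting but are not supported:

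- **That section 9.1.1 contradicts item 5.** It governs optional suspension and can be read as a separate, lower tier with its own route for resuming. The medical monitor is involved under every route. Only the boundary between the two needs stating.
- **That some proteinuria results meet the rule in one unit but not the other.** The two unit forms are joined by an or, so meeting either triggers the rule. The size of any gap would also rest on a conversion factor that the documents do not give. The differing signs matter only at one exact value.
- **That the effect can be sized from the arm size.** The share of a 25-participant arm that one person represents says nothing about how many participants, if any, would have a qualifying renal result that also falls within an exception.

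**Conclusion.** The point holds as an internal inconsistency of wording. For renal abnormalities, item 5 of Protocol section 9.1 gives two instructions that differ in the two cases covered by the renal exceptions, and the scope of the closing note is not stated. It is worth correcting because it concerns a safety stopping rule and the correction is cheap.

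The conclusion assumes that the note is read on its plain wording, as applying to any abnormality under item 5. It also assumes that the exception clause covers both creatinine and proteinuria. If the clause were attached to proteinuria alone, the conflict would remain for proteinuria.

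The number of participants affected is unknown and may be small or zero. No power, sample-size or error-rate figure changes. Membership of the full analysis set does not change either, because Protocol 11.2 requires only randomisation to a blinded arm and one dose. The effect on the analysis is limited to who is counted as discontinued and who is counted as treated per protocol. Nothing here bears on which clinical rule or threshold is right.

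**What to change.** Reconcile the renal bullet of item 5 with the note that closes it. State whether the note applies to renal values and, if it does, how it relates to the renal exceptions. Each combination of abnormality (renal or liver) and causality should then have one stated outcome.

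In the same edit:

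- state whether resumption after an item 5 stop follows the route in the closing note or the one in section 9.1.1;
- reconcile the inequality signs in the paired protein:creatinine thresholds.

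The content of each rule is for the sponsor and its clinical advisers to decide. The cost is a change of protocol wording and a memo to sites. No analysis or sample-size calculation has to be redone.

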9.1.1. Temporary Discontinuation

Study drug dosing may be temporarily suspended in the event of:

1. Clinically important laboratory abnormalities
2. Other intercurrent illnesses or major surgery
3. Use of prohibited treatment
4. Any other protocol deviation that results in a significant risk to the participant's safety
5. Sponsor decision

After a laboratory abnormality leading to a delay of dosing normalises sufficiently, study treatment may resume at the discretion of the principal investigator in consultation with the medical monitor. Similarly, study treatment may resume after the medication leading to suspension of dosing is discontinued. A decision to discontinue study drug and/or to reinstitute study treatment should be discussed with the medical monitor. The investigator may suspend study treatment at any time, even without consultation with the medical monitor if the urgency of the situation requires immediate action and if this is determined to be in the participant's best interest. However, the medical monitor should be contacted as soon as possible in any case of study drug discontinuation.

